17.0 Data Management* and Confidentiality

- 17.1* Summary statistics will be described by using means and standard deviation for parametric variables and median with interquartile ranges (IQRs) for nonparametric variables. The Kolmogorov-Smirnov test will be used to assess the normality of data. Bivariate analysis for paired continuous variables will be conducted using the paired t test and Wilcoxon signed-rank test, and for independent continuous variables it is conducted using the independent samples t-test and Wilcoxon rank-sum test. Bivariate analysis for categorical variables will be conducted using the Chi-square test or Fisher's exact test, where appropriate. P value less than 0.05 is considered to indicate statistical significance. Statistical analysis will be done using SAS 9.4 and G*Power version 3.1.9.2.

Primary Outcome: The primary outcome is the proportion of full stomach state.

- 17.2* Research records will be stored in a locked cabinet and password protected computer. Only certified research personnel will be given access to identifiable subject information
- 17.3* Following publication of study results, research records will be stored for a period of 3-5 years and then will be destroyed by placing in a secure shredding bin.

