1.0 Study Summary

Study Title	Ultrasonographic evaluation of gastric volume and contents before surgery in children
Study Design	Prospective, non-blinded observational study
Primary Objective	The primary objective of this study is to evaluate gastric volume and contents in patients who are scheduled for elective, urgent, and emergent surgery
Secondary Objective(s)	None
Research Intervention(s)/ Investigational Agent(s)	There will be no change in anesthetic management or use of investigational agents.
IND/IDE #	Not applicable
Study Population	Patients who are scheduled for elective, urgent or emergent surgery
Sample Size	300 (100 in each group)
Study Duration for individual participants	Less than 10 minutes
Study Specific Abbreviations/ Definitions	CSA=cross sectional area POCUS=Point-of-Care Ultrasound RSI=Rapid Sequence Induction RLD=right lateral decubitus

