2.0 Objectives

- 2.1 The primary objective of this study is to evaluate gastric volume and contents as well as gall bladder size in patients scheduled for routine, urgent, and emergency surgery.
- 2.2 The hypothesis is that patients with stress, pain and opioid administration will have delayed gastric emptying and therefore a larger gastric fluid volume than those scheduled for elective surgery. The patients who have an appropriate NPO time will have a larger gallbladder size than the patients with shorter NPO time.

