3.0 Background

- 3.1 Point-of-Care Ultrasonography (POCUS) has been recognized as a powerful tool to evaluate critically ill patients. Using gastric ultrasonography, we can evaluate gastric volume and the types of contents as well as gall bladder size. The cross-sectional area of the gastric antrum is used to calculate the gastric volume. The full stomach state in pediatric patients scheduled for elective surgery is low at only 0-1%. However, it is unknown how lack of appropriate NPO time affects gastric volume and contents as well as gall bladder size. The gallbladder stores bile and starts to empty after the presence of fatty food in duodenum. Gallbladder emptying also

requires relaxation of the sphincter of Oddi, which may be disturbed by opioids. Therefore, it may be useful to evaluate patient NPO status. The diameter of great vessels has been used to evaluate patient volume status in pediatric patients.

- 3.2 Point-of-care gastric ultrasound had a sensitivity of 1.0 and a specificity of 0.975 to detect a “full stomach”. ¹ Using point-of-care gastric ultrasound, a previous study reported that 0-1 % of the healthy pediatric patients scheduled for elective surgery were at risk of pulmonary aspiration ^{2 3} However, 35 % of the adult patients scheduled for unplanned surgery had a full stomach even after ≥ 6 hours of NPO time ⁴ The normal gallbladder sizes in healthy children has been evaluated after fasting in previous report. ⁵ There is no article which reports the relationship between NPO state and gallbladder size.
- 3.3 Rapid sequence induction (RSI) is widely used to avoid pulmonary aspiration during anesthetic induction. However, RSI is the risk factor for oxygen desaturation and other airway complications when compared to standard anesthetic induction techniques. The current study will help identify which trauma patients are truly at risk for aspiration and therefore require RSI.

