4.0 Study Endpoints

- 4.1 The primary study endpoint is the number (percentage) of patients in the urgent, emergent group with a full stomach state as assessed by gastric volume and contents despite an appropriate NPO time.
- 4.2 The secondary endpoint will be to determine gall bladder size between fasted patients undergoing elective versus urgent/emergent surgery. The other endpoint will be to evaluate the preoperative volume status.

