10.0 Inclusion and Exclusion Criteria*

10.1 Potential subjects will be identified by reviewing the surgery schedule in Epic and will be recruited from the main OR pre-operative area the day of their surgery.

10.2 Inclusion criteria: ASA 1-3 patients aged 2-18 years of scheduled for elective, urgent, or emergent surgery under general anesthesia.

Exclusion criteria: History of upper gastro-intestinal surgery.

10.3 We will include children, and will not include adults unable to consent, pregnant woman, and prisoners as they are not part of our usual patient population.

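### Hypothesis 2.2 compares gastric fluid volume between non-randomised urgency groups, but section 17.1 offers only unadjusted tests, so a difference in fasting time or age could be read as delayed emptying.

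*Combined protocol and SAP*

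**What the plan says.** The study is observational, with 100 patients planned in each of three urgency groups (sections 1.0 and 12.1).

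- **Volume is central to the aim.** The primary objective in section 1.0 is to "evaluate gastric volume and contents in patients who are scheduled for elective, urgent, and emergent surgery". The hypothesis in 2.2 is causal: stress, pain and opioids lead to "delayed gastric emptying and therefore a larger gastric fluid volume than those scheduled for elective surgery". Section 4.0 does not list gastric volume as an endpoint.
- **The tests are unadjusted.** Section 17.1 is a general list that ties no test to a named variable. Its entry for this kind of comparison is that "for independent continuous variables it is conducted using the independent samples t-test and Wilcoxon rank-sum test". No regression, stratification or matching is described anywhere.
- **Fasting is left free for volume.** Section 10.2 admits "ASA 1-3 patients aged 2-18 years of scheduled for elective, urgent, or emergent surgery under general anesthesia", with no fasting time. Section 2.2 expects fasting to vary, since adequately fasted children "will have a larger gallbladder size than the patients with shorter NPO time". Section 3.1 says "it is unknown how lack of appropriate NPO time affects gastric volume and contents as well as gall bladder size".
- **The fasting conditions lie elsewhere.** Section 4.1 concerns patients "with a full stomach state as assessed by gastric volume and contents despite an appropriate NPO time", and section 4.2 is "to determine gall bladder size between fasted patients undergoing elective versus urgent/emergent surgery". Neither governs the volume comparison.
- **The covariates exist.** Section 6.1 records age, NPO time, symptoms and opioids. Section 17.1 gives them no role in a model.

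**The concern.** The volume in the stomach before surgery depends on how fast it empties and on how long it has had to empty. Section 2.2 makes a claim about the first. A t-test or rank-sum test between urgency groups mixes the two, and also mixes in any difference in age across a range of 2 to 18 years.

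If children having unplanned surgery have fasted for less time, a larger volume in that group may show only that. If they have fasted longer, a real delay may be understated, depending on how volume falls with time. The planned tests cannot tell these explanations apart, although the information needed is on the case record. Adjustment added after the data are seen would leave the covariates and their form open to choice.

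**Working it through.** **No planned figure to reproduce.** The sample size of 300 comes with no SD, effect size or power. No passage gives a fasting gap, an age gap or a slope of volume on either. Every bias input below is therefore an assumption.

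**Step 1: unadjusted test with a confounding shift.** Inputs: 100 elective v 200 urgent plus emergent patients (section 12.1, pooled as in 4.2), and alpha 0.05 (section 17.1; two-sided assumed). With no true effect and a confounding shift of δ SD, the t statistic is noncentral on 298 df, with λ = δ / √(1/100 + 1/200) = δ / 0.1225.

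| δ (SD) | λ | Significant |
|---|---|---|
| 0 | 0 | 5.0% |
| 0.12 | 0.98 | 16.4% |
| 0.24 | 1.96 | 49.7% |
| 0.35 | 2.86 | 81.3% |

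**Step 2: what could give such a shift.** Assume volume falls 0.03 ml/kg per fasting hour, the residual SD is 0.4 ml/kg, and unplanned patients have fasted 2 h less. Then δ = 0.03 × 2 / 0.4 = 0.15 SD; at a 4 h gap it is 0.30 SD. At SD 0.8 the shifts halve to 0.075 and 0.15 SD. Simulation used 2,000 studies per scenario, skewed errors, and NPO SDs of 2 h (elective) and 3 h (unplanned). The t-test rejected in about 23% (2 h) and 67% (4 h) of studies at SD 0.4, and in about 10% and 24% at SD 0.8. A robust linear model on group, age and a four-knot spline of NPO time stayed at about 4–5%.

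**Step 3: does this depend on a straight line?** Replace it with an assumed exponential fall, 1.5 × exp(−h/2). At SD 0.4 the t-test still rejects in about 23% (2 h) and 86% (4 h). Adjusting with a linear NPO term leaves about 19–20% at the 4 h gap; the spline gives about 5–6%. At a 2 h gap the linear and spline terms both hold about 5%.

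**Step 4: the opposite direction.** Assume a true excess of 0.2 ml/kg, SD 0.4, and unplanned patients fasted 2 h or 4 h longer.

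| Assumed fall in volume | Power unadjusted (2 h / 4 h) | Power adjusted (2 h / 4 h) |
|---|---|---|
| Straight line, 0.03 per hour | 80% / 37% | 95% / 89% |
| Exponential, same rate in both groups | 97% / 92% | 96% / 90% |
| Exponential, time constant 4 h unplanned v 2 h elective | 62% / 20% | 90% / 72% |

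Masking appears in the first and third rows and vanishes in the second.

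**Step 5: age.** The formula in section 6.2 is (−7.8 + 0.035 × CSA + 0.127 × months) / kg. The weights here are assumed.

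- CSA 200 mm²: at 2 years, 12 kg, (−7.8 + 7.0 + 3.048) / 12 = 0.19 ml/kg. At 10 years, 32 kg, (−7.8 + 7.0 + 15.24) / 32 = 0.45 ml/kg.
- CSA 400 mm²: at 2 years, (−7.8 + 14.0 + 3.048) / 12 = 0.77 ml/kg. At 10 years, (−7.8 + 14.0 + 15.24) / 32 = 0.67 ml/kg.

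Calculated volume rises with age at one antral area and falls at the other. Age matters, but the sign of its effect is not fixed.

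**The case against.** **Volume is not a listed endpoint, and 17.1 assigns it no test.** Both are true, so this is not an error in the primary test. But volume is in the primary objective and is the outcome that 2.2 predicts. A reported volume comparison will be read as testing 2.2, and 17.1 provides nothing else for it.

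**The unadjusted comparison is a legitimate description.** It shows what volumes are found in each group as patients present, which serves objective 2.1. That stands, and is why the bivariate tests should be kept. It does not serve the causal statement in 2.2.

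**All bias inputs are assumed.** This also stands. A reader might infer from the percentages that a false-positive result is likely, or that unplanned patients have fasted less. The documents support neither, because they give no fasting gap and no direction.

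**Masking.** A reader might infer that imbalance would generally hide a real delay. Step 4 shows that this depends on the shape of the fasting-volume relation, which the documents do not describe.

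**The model is a simplification.** If emptying is truly slower in one group, the difference varies with fasting time. A single group coefficient is then an average over the fasting times observed and should be described so. Robust errors and a spline are one reasonable choice among several.

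**Conclusion.** The point holds as a gap in the analysis of hypothesis 2.2. The groups are not randomised, fasting time is unrestricted for volume, only unadjusted tests are offered, and the covariates needed are already recorded. A difference in NPO time or age could create an apparent effect and, under some shapes, could hide a real one.

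The size and direction are unknown. The 16%, 50% and 81% figures rest on assumed shifts of 0.12, 0.24 and 0.35 SD, a two-sided test, and urgent and emergent patients pooled. The simulations rest on assumed SDs, slopes and gaps.

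A reader might extend the criticism to the primary endpoint. The documents do not support that on these grounds: it is a full-stomach proportion, and 4.1 already conditions it on fasting. It is outside this point.

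The change should be made, but the study's primary result does not hinge on it.

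**What to change.** Add a paragraph to section 17.1.

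1. Keep the bivariate tests for volume as descriptive, and tabulate NPO time and age by urgency group so that overlap can be seen.
2. Make the inferential analysis of gastric volume (ml/kg) a prespecified linear model with robust standard errors on urgency group, NPO time and age. Allow a non-linear NPO term, for example a restricted cubic spline with knots fixed in advance, because a linear term can leave residual confounding when the fasting gap is large (step 3).
3. Do not adjust for opioids or symptoms in that model. Section 2.2 names pain and opioids as causes, and adjusting for them would remove part of the effect under study. Examine them as exposures in a separate model adjusted for NPO time and age.

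The cost is slightly more analysis, with no new data, visits or patients. Some precision is lost when fasting times overlap little. In the SD 0.4 example the standard error of the group difference rises from 0.050 to 0.054 ml/kg at a 2 h gap (0.054 / 0.050 = 1.08) and to 0.063 at 4 h (0.063 / 0.050 = 1.26). Adjustment covers NPO time and age only; other differences between the groups would remain.

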18.0 Provisions to Monitor the Data to Ensure the Safety of Subjects*

The study will only be monitored by the study investigators.

19.0 Provisions to Protect the Privacy Interests of Subjects

19.1 Subject information will not be given to any other investigators.

Subjects and their information will be closely monitored and guarded by study staff; there will be limited access to patients and their information by trained study staff; and subject information will only be shared and discussed between study staff specific to this study.

20.0 Compensation for Research-Related Injury

N/A

21.0 Economic Burden to Subjects

N/A

22.0 Consent Process

22.1 We are requesting a waiver of informed consent documentation.

Subjects will receive a complete explanation of the study and will be asked to consent verbally. Subjects will receive a written summary of the research as outlined in the attached written Study Information Sheet. Subjects will not be asked to sign a consent form.

23.0 Process to Document Consent in Writing

N/A

24.0 Setting

The research team will identify the potential subjects in anesthesia office by Epic and recruit them in the preoperative area. Research procedures will be performed in the pre-operating room.

25.0 Resources Available

25.1 We will need approximately 20 minutes per patient to explain the research protocol, obtain consent, and enroll patients. The Department of Anesthesiology and Pain Medicine has 2 research coordinators/RNs and 2 research associates that will be enrolling subjects for this study. All study staff will be trained on the study procedures.

Before the study start, the study protocol, the research procedures, research member's duties, and functions will be informed by e-mail. After the e-mail is sent, the research meeting will be held.

26.0 Multi-Site Research*

N/A

27.0 Protected Health Information Recording

1.0 Indicate which subject identifiers will be recorded for this research.

- Name
- Complete Address
- Telephone or Fax Number
- Social Security Number (do not check if only used for ClinCard)
- Dates (treatment dates, birth date, date of death)
- Email address, IP address or url
- Medical Record Number or other account number
- Health Plan Beneficiary Identification Number
- Full face photographic images and/or any comparable images (x-rays)
- Account Numbers
- Certificate/License Numbers
- Vehicle Identifiers and Serial Numbers (e.g. VINs, License Plate Numbers)
- Device Identifiers and Serial Numbers
- Biometric identifiers, including finger and voice prints
- Other number, characteristic or code that could be used to identify an individual
- None (Complete De-identification Certification Form)

2.0 Check the appropriate category and attach the required form* on the Local Site Documents, #3. Other Documents, page of the application. (Choose one.)

- Patient Authorization will be obtained. (Include the appropriate HIPAA language (see Section 14 of consent template) in the consent form OR attach the HRP-900, HIPAA AUTHORIZATION form.)
- Protocol meets the criteria for waiver of authorization. (Attach the HRP-901, WAIVER OF HIPAA AUTHORIZATION REQUEST form.)
- Protocol is using de-identified information. (Attach the HRP-902, DE-IDENTIFICATION CERTIFICATION form.) (Checked "None" in 1.0 above)
- Protocol involves research on decedents. (Attach the HRP-903, RESEARCH ON DECEDENTS REQUEST form.)
- Protocol is using a limited data set and data use agreement. (Contact the Office of Technology Commercialization to initiate a Limited Data Use Agreement.)

***Find the HIPAA forms in the IRB Website Library, Templates.**

Attach the appropriate HIPAA form on the “Local Site Documents, #3. Other Documents”, page of the application.

3.0 How long will identifying information on each participant be maintained?

Following publication of study results, research records will be stored for a period of 3-5 years and then will be destroyed by placing in a secure shredding bin.

4.0 Describe any plans to code identifiable information collected about each participant.

N/A

5.0 Check each box that describes steps that will be taken to safeguard the confidentiality of information collected for this research:

- Research records will be stored in a locked cabinet in a secure location
- Research records will be stored in a password-protected computer file
- The list linking the assigned code number to the individual subject will be maintained separately from the other research data
- Only certified research personnel will be given access to identifiable subject information

6.0 Describe the provisions included in the protocol to protect the privacy interests of subjects, where "privacy interests" refer to the interest of individuals in being left alone, limiting access to them, and limiting access to their information. (This is not the same provision to maintain the confidentiality of data.)

Subject information will not be given to any other investigators. Subjects and their information will be closely monitored and guarded by study staff; there will be limited access to patients and their information by trained study staff; and subject information will only be shared and discussed between study staff specific to this study. Describe the steps that will be taken to protect subjects' privacy interests. "Privacy interest" refers to a person's desire to place limits on whom they interact or whom they provide personal information.

Confidential Health Information

1.0 Please mark all categories that reflect the nature of health information to be accessed and used as part of this research.

- Demographics (age, gender, educational level)
- Diagnosis
- Laboratory reports
- Radiology reports
- Discharge summaries
- Procedures/Treatments received
- Dates related to course of treatment (admission, surgery, discharge)
- Billing information
- Names of drugs and/or devices used as part of treatment

- Location of treatment
- Name of treatment provider
- Surgical reports
- Other information related to course of treatment
- None

2.0 Please discuss why it is necessary to access and review the health information noted in your response above.

